#### **7.7.1.10 Transvaginal Ultrasound**

For subjects with uterus and/or ovaries for whom TVUS have been performed, interpretation of TVUS image results will be summarized by frequency counts and percentages at baseline and post-dose scheduled visits (in non-hysterectomized subjects) for the Safety Analysis Set.

A shift table will be produced to summarize change in frequency counts (n) and percentages of subjects with normal, abnormal without clinical significance, and abnormal with clinical significance TVUS image interpretation from baseline to post-dose scheduled visits (in non-hysterectomized subjects) for the Safety Analysis Set.

A listing will be provided for TVUS data for the Included Set.

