10.1.6.6. Visit 6: End of Trial/Early Termination Visit (week 53 or earlier)

Subjects will return to the trial site in week 53 for Visit 6. This will be the EoT and follow-up procedures will be performed. Subjects will take their last daily dose of the trial medication on the evening before the EoT visit.

For subjects who terminate early every reasonable effort should be made by the investigator to complete the final assessment procedures as specified in this section (see also Section 8.3). In case of early termination treatment may have been stopped earlier.

The following observations/procedures are to be performed and checked at Visit 6:

- Physical examination
- Gynecological examination
- Breast examination
- Digitalized mammography (in case of early termination, mammography may only be performed if subjects was treated for at least 12 weeks and last mammography was taken at least 9 months earlier)
- Vital signs
- 12-lead ECG
- Endometrial biopsy if the subject has at least completed 12 weeks of treatment (for non-hysterectomized women only)
- TVUS (for women who still have uterus and/or ovaries)
- MENQOL and CGI questionnaires
- Fasted blood sampling for:
 - Routine hematology, chemistry
 - Lipid metabolism
 - Glucose metabolism
 - Additional optional analysis
- Review of returned trial medication/drug accountability
- Dispense trial medication (P4 200 mg for non-hysterectomized subjects only)
- Record prior/concomitant medication
- Record AEs
- Complete end of trial form (hysterectomized subjects only)

For hysterectomized subjects: after completion of the Visit 6 procedures in the Safety Study part, the subject has completed the trial.

For non-hysterectomized subjects: after completion of Visit 6 procedures the subjects will start treatment with 200 mg P4 once daily for 14 days. Subjects should take the progestin medication as per investigator's instructions. Subjects are instructed to record the vaginal bleeding events and P4 intake in the diary. Subjects will return to the clinic approximately 10 days after completion of the progestin treatment for the endometrial safety follow-up visit (Visit 7).

10.1.6.7. Visit 7: Non-hysterectomized Subjects Only: Endometrial Safety Follow-up Visit (week 55/56 or earlier)

The following observations/procedures are to be performed and checked at Visit 7:

- TVUS
- Return of diary
- Review of diary
- Review returned unused medication/drug accountability
- Record concomitant medication
- Record AEs

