10.4. Safety Assessments

Safety evaluations will include the following:

- General safety will be assessed in terms of occurrence of TEAS (including SAE monitoring)
- Physical and Gynecological examination (including TVUS for safety assessment)
- Breast examination
- Vital signs
- ECG
- Routine Clinical Laboratory Tests
- Mammography
- Endometrium thickness measured by TVUS (non-hysterectomized subjects only)
- Endometrial biopsies (non-hysterectomized subjects only)
- Vaginal bleeding events (non-hysterectomized subjects only)

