10.4.7. Transvaginal Ultrasound in Non-hysterectomized Subjects

A TVUS will be performed during screening and at the EoT visit in all subjects who still have uterus and/or ovaries for general safety assessment.

In addition TVUS will be performed to monitor the endometrium thickness during the treatment at Visit 4, Visit 5 and Visit 6 in the Efficacy Study part and Visit 3, Visit 4 and Visit 5 in the Safety Study part. The TVUS will be done in the sagittal section showing the cervix including

the cervical canal. The TVUS will be assessed by the Investigator, gynecologist or designee and bi-layer endometrial thickness will be measured.

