- e) Blood pressure, heart rate, body height (during screening only) and body weight (during screening and EoT only).
- f) To be performed in subjects with uterus and/or cervix, unless a written normal result is available within 18 months before screening start. The PAP test may be repeated once in case of inadequate or insufficient sample.
- g) Unless a written normal result, including digital imaging, is available within 9 months before screening start.
- h) Mammography at EoT visit may only be performed if the subject was treated for at least 12 weeks and the last mammography was taken at least 9 months earlier.
- i) If the subject is not fasting, a new appointment needs to be made as soon as possible. Laboratory tests may be repeated once during the screening period, at the discretion of the investigator.
- j) Additional blood samples, including one DNA sample at Visit 1 only, will be collected for optional additional analysis of in the context of this program or any further research on E4.
- k) A pregnancy test may be performed at the discretion of the Investigator.
- l) TVUS at screening and EoT will be taken for all subjects who still have a uterus and/or ovaries. At all other time points a TVUS will be performed to monitor the endometrium thickness only for subjects who still have a uterus.
- m) Visit 7 for non-hysterectomized subjects only at approximately 10 days after completion of the progestin treatment.
- n) Non-hysterectomized subjects only.
- o) If the subject was treated for at least 12 weeks.
- p) Subjects are instructed during screening on how to fill in the diary and if needed can be re instructed.
- q) At each visit the diary will be checked. Completed pages will be collected and will remain at the study site.
- r) Progestin treatment for non-hysterectomized subjects only.
- s) If lipid and/or glucose parameters could be a reason of concern in the judgement of the Investigator, fasted blood sampling for lipid and glucose parameters assessment may be done during the Washout Visit. Otherwise, this assessment will be done during the Screening Period.
- t) Laboratory tests may be repeated once during the screening period, at the discretion of the investigator. FSH measurement is not required for subjects with bilateral oophorectomy.
- u) In the event screening requirements cannot be met within 4 weeks, the screening period may be extended with prior Medical Monitor approval, but screening period may not exceed 8 weeks.

---

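### As worded, SAP 7.7.1.10 keeps the end-of-treatment ultrasound results of hysterectomized women with ovaries out of both TVUS tables, although both schedules require those scans

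*SAP*

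**What the plan says.** **Who is scanned.** Protocol section 10.4.7 states: "A TVUS will be performed during screening and at the EoT visit in all subjects who still have uterus and/or ovaries for general safety assessment". The Visit 6 procedures in protocol section 10.1.6.6, which also serve as the early termination visit, list "TVUS (for women who still have uterus and/or ovaries". Footnote l of the protocol's Safety Study part schedule (section 2.2) gives the same rule, and SAP Appendix 2 repeats it: "TVUS at screening and EoT will be taken for all subjects who still have a uterus and/or ovaries". That footnote limits the scan to women with a uterus only at the other time points.

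**What is tabulated.** SAP section 7.7.1.10 begins "For subjects with uterus and/or ovaries for whom TVUS have been performed". It then says that the image interpretation will be "summarized by frequency counts and percentages at baseline and post-dose scheduled visits (in non-hysterectomized subjects) for the Safety Analysis Set". The shift table covers "TVUS image interpretation from baseline to post-dose scheduled visits (in non-hysterectomized subjects) for the Safety Analysis Set". The section ends: "A listing will be provided for TVUS data for the Included Set".

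SAP section 8, which records changes from the protocol's planned analysis, does not mention leaving any women out of the TVUS tables.

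**The concern.** The opening of 7.7.1.10 and its parenthesis name different populations. A programmer who follows the parenthesis literally will drop hysterectomized women from every post-dose TVUS cell, including EoT and ED, where the schedule requires them to be scanned if they have ovaries. In these women the scan cannot be about the endometrium. It is there for general safety, which in practice means the ovaries and pelvis. A required safety assessment would be collected and listed, but its change from baseline would not be summarized in the one table designed to show it.

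**Working it through.** No sample size, power or error-rate figure bears on this point, and the plan gives no figure to reproduce. The check compares who is scanned with who is tabulated, and then sizes the gap.

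**1. Can hysterectomized women with ovaries be in the Safety Study part?** Yes. Inclusion criterion 9b (protocol section 8.2.1) accepts FSH and E2 levels as an alternative to bilateral oophorectomy.

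**2. Which scheduled post-dose scans do they have?**

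| Scheduled post-dose visit | Scanned under footnote l | Post-dose TVUS tables as worded |
|---|---|---|
| Visits 3, 4, 5 | Women with a uterus | Non-hysterectomized |
| Visit 6 (EoT/ED) | Women with a uterus and/or ovaries | Non-hysterectomized |
| Visit 7 | Non-hysterectomized only | Non-hysterectomized |

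The two columns disagree only at Visit 6. That is the only scheduled post-dose scan for hysterectomized women with ovaries, so the restriction removes all of their scheduled post-dose results from both tables. Canadian sites enroll only hysterectomized women (protocol section 16.5.1), so no post-dose scan from those sites would be tabulated.

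**3. Does another planned output carry these results?**
- Endometrial thickness (SAP 7.7.1.11): non-hysterectomized women only.
- Gynecological examination (SAP 7.7.1.7): no restriction by hysterectomy status, but no mention of TVUS. Protocol section 10.4.2 describes that examination as manual.
- TVUS listing: yes, subject by subject.
- Adverse event tables: in part. Protocol section 10.4.1 requires adverse events to be recorded however they are detected. SAP 7.7.1.1 tabulates the reproductive system and breast class by hysterectomy status. However, SAP Table 1 counts an event with a known start date as treatment-emergent only if that date falls before the last visit, which for hysterectomized women is EoT or ED. A finding dated on the day of that scan does not qualify. In a non-hysterectomized woman the same finding can qualify, because her last visit is the later follow-up. A shift from normal to abnormal but not clinically significant is not, as such, an adverse event.

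**4. How many scans?** Inputs: about 200 hysterectomized women (SAP 3.1) and 50% dropout at 12 months (protocol section 8.1, not split by hysterectomy status). The share with at least one ovary is not stated, so it is varied as an assumption.

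Hysterectomized completers = 200 × (1 − 0.50) = 100.

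| Assumed share with ovaries | EoT scans outside the TVUS tables |
|---|---|
| 25% | 100 × 0.25 = 25 |
| 50% | 100 × 0.50 = 50 |
| 75% | 100 × 0.75 = 75 |

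At 50% dropout the possible range is 0 to about 100. ED scans come on top. Their number depends on how many of the other 200 − 100 = 100 women attend that visit, which the documents do not give.

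**The case against.** **The parenthesis may be a slip.** It may be a misplaced copy of the footnote rule for mid-treatment visits, and the heading of protocol section 10.4.7 itself refers to non-hysterectomized subjects. This is plausible, and nothing shows that the exclusion was deliberate. As printed, though, the words cover every post-dose scheduled visit, and SAP section 8 offers no reason. An accident should be corrected and a choice explained.

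**The data are not lost.** This stands. Every scan is listed, and the baseline scans of hysterectomized women can be read as included in the baseline counts. The gap is a missing post-dose tabulation.

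**Clinically significant findings have another route.** This stands in part. Findings recorded as adverse events with a start date before the last visit would appear, by hysterectomy status, in the reproductive system tables. A reader might infer that a new ovarian finding could appear in no planned table at all. The documents do not support that. What is missed is narrower: findings dated on the EoT or ED day, and changes judged not clinically significant.

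**TVUS is not a named primary endpoint.** This also stands. A reader might infer that a primary endpoint result is being dropped, because protocol section 10.4 lists "Physical and Gynecological examination (including TVUS for safety assessment" and changes in gynecological examination are a primary endpoint of the Safety Study part. The endpoint text does not name TVUS, however, and protocol section 10.4.2 does not include it in that examination. If TVUS does belong there, the unrestricted gynecological tables should carry it. If it does not, it lies outside the named endpoint. Neither reading gives a primary endpoint loss.

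**Conclusion.** The point holds as an inconsistency within the SAP, and between the SAP and both schedules, with a definite effect on outputs. If 7.7.1.10 is programmed as worded, the scheduled post-dose scans of hysterectomized women with ovaries are listed but enter neither TVUS table. This conclusion rests on the text alone.

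The size is uncertain: about 25, 50 or 75 EoT scans at an assumed 25%, 50% or 75% with ovaries, within a range of 0 to about 100, plus ED scans. It also assumes that the 50% dropout applies equally to both strata.

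A reader might further infer that an excess of ovarian findings on E4 20 mg would be missed. The Safety Study part has one open-label arm and no formal testing, so even the corrected table would describe change from baseline without a comparator and could not show an excess. What is at stake is complete descriptive reporting of a required safety assessment.

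**What to change.** In SAP 7.7.1.10, limit the parenthesis to Visits 3, 4, 5 and 7. For EoT and ED, present the frequency summary and the baseline-to-EoT/ED shift for all women scanned, by hysterectomy status, in line with SAP section 7.8. If the exclusion is intended, state it and its reason in SAP section 8.

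The correction costs one wording change and one table column. The scans are already scheduled and recorded, so it needs no new data and adds nothing for participants.

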#### **7.7.1.11 Endometrial Thickness Measured by Ultrasound**

TVUS will be performed to monitor the endometrium thickness during the treatment at Visit 3, 4, 5 and 6 for non-hysterectomized subjects.

Descriptive statistics of observed values and change from baseline (n, mean, SD, median, min, and max) for endometrial thickness measured by ultrasound will be provided by visit for the Safety Analysis Set.

A line plot for change from baseline over time for endometrial thickness measured by ultrasound will be provided.

A listing will be provided for endometrial thickness measured by ultrasound for the Included Set.

#### **7.7.1.12 Endometrial Biopsy**

The frequency of endometrial events will be computed on the evaluable biopsies of the endometrium (Initial and Final diagnosis) or adequate specimens (Safety) as well as non-evaluable and inadequate (respectively) biopsies. In addition, count and percentage will be provided for the sub-categories of the evaluable/adequate biopsies. The incidence of

---

spotting/bleeding will be analyzed by a 28-day period. The rate of endometrial events will be computed on the evaluable endometrium. The 95% two-sided CIs will be computed on the observed frequency of hyperplasia/carcinoma of the endometrium.

#### **7.7.1.12.1 Evaluation of Endometrial Tissue**

Standardized criteria as provided in Blaustein's pathology text (Pathology of the Female Genital Tract 8, see [Appendix 5](#)) will be used for the characterization of the endometrial tissue. Endometrial polyps will be fully characterized as to the glandular proliferation and atypia (see [Appendix 5](#) for additional histologic characteristics of the specimen).

The endometrial tissue obtained by endometrial biopsy at screening, during the conduct of the study, and at the end of the study will all be processed in the same manner by a central laboratory.

#### **Screening Biopsies/Initial Diagnosis:**

Biopsies obtained at screening will be initially read by one safety pathologist (initial pathology report). The Investigator will decide on inclusion of the subject into the study, or screen failure, based on the initial pathology report at screening.

All inadequate tissue records will be disregarded in the derivation of the Initial diagnosis; the diagnosis will be based on only adequate tissue samples read by the one safety pathologist.

Screening biopsies will also be read by two other expert pathologists after enrollment. If a subject is enrolled incorrectly (e.g. based on an inadequate sample) she will be discontinued .

#### **On Study Biopsies:**

Biopsy samples collected during the study and at the end of treatment/early discontinuation (Visit 6) will be read by three expert pathologists for the Safety and Final/Consensus diagnosis. These three expert pathologists will be independent and belong to different institutions. They will be blinded to each other's readings. The Safety diagnosis will be based on readings from pathologists 1, 2 and 4, whereas the Final/Consensus diagnosis will be based on readings from pathologists 2, 4 and 5. During the study, the investigator will be informed if subsequent readings impact the initial decision.

Note, endometrial biopsy will be performed at end of treatment visit if the subject was treated for at least 12 weeks.

Using Blaustein's classification, Benign Endometrium has been defined as any of the following readings: no tissue, insufficient tissue, atrophic endometrium, inactive endometrium, proliferative endometrium (incl. weakly proliferative, active proliferative, disordered proliferative), secretory endometrium (incl. cyclic type, progestational type) and menstrual type endometrium. For the detail of other category, please find Category Indicators for Final Diagnosis in [Appendix 5](#).

#### **Safety Diagnosis:**

The investigator will receive final pathology report (or Safety diagnosis) defined as the worst

reading of adequate specimens from the 3 pathologists involved in safety reading, where disordered proliferative is the best and carcinoma the worst. In case none of the adequate specimen readings are disordered proliferative or worse, the first reading with adequate specimen will be kept as Safety diagnosis. If the 3 readers concur on 'no tissue or tissue insufficient' then no Safety diagnosis is derived.

All inadequate tissue records will be disregarded in the derivation of the Safety diagnosis; the diagnosis will be based on all available adequate tissue samples, from any number of readers.

A reading of disordered proliferative endometrium, hyperplasia or carcinoma from any of these pathologists will prompt the exclusion or discontinuation of the subject from the study.

[figure not shown]
#### **Final/Consensus Diagnosis:**

The Final/Consensus diagnosis is the concurrence of at least 2 adequate specimens from the 3 pathologists. If there is no agreement among at least 2 pathologists, the most severe pathologic diagnosis will be used as the Final/Consensus diagnosis. If the 2 or 3 readers concur on 'no tissue or tissue insufficient' then no Final/Consensus diagnosis will be derived.

The Final/Consensus diagnosis will only be derived for evaluable biopsies. All inadequate tissue records will be disregarded; evaluable biopsies are defined as at least 2 readers assessing adequate tissue samples.

The Final/Consensus diagnosis will be used for the analysis of the endometrial safety endpoint. The categorization for Final/Consensus diagnosis is defined on [Figure 2](#).

**Figure 2 : Category Indicators for Final Diagnosis (from less to most severe)**

#### **Discontinuation:**

If a biopsy shows disordered proliferative endometrium, hyperplasia or carcinoma, the study drug will be stopped, the treatment with 200 mg P4 for 14 days will be given and the subject will return to the site for the last visit. If the event is not resolved, the subject will be followed up until resolution according to local practice/guidelines.

Starting from Protocol Version 7.1 (Amendment 6.1) disordered proliferative endometrium is not considered as a reason for the exclusion or discontinuation of the subject from the study.

The subject with disordered proliferative endometrium will continue in the trial with regular follow-up according to the Protocol.

In case of bleeding events grade 2, disordered proliferative endometrium or worse, the event must be reported as an AESI and the Sponsor will be notified.

### 7.7.1.12.2 Analysis of Endometrial Tissue

All the analyses of endometrial tissues will be performed only for non-hysterectomized subjects.

- Initial diagnosis (from first safety reader, based on adequate samples only)
  - By visit analysis: The Initial diagnosis will be summarized at each visit.
- Safety diagnosis
  - By visit analysis: The Safety diagnosis will be summarized at each visit.
- Final/Consensus diagnosis
  - By visit analysis: The Final/Consensus diagnosis will be summarized at each visit performed on-treatment.
  - Worst case analysis across all visits: The worst case derived from all on-treatment visits, including unscheduled visits, will be summarized for Final/Consensus diagnosis.

Visits will be clustered as specified in [Table 6](#) of Appendix 1.

Frequency counts (n), percentages and the 95% CIs of the histologic characteristics of the endometrium including no tissue, tissue insufficient for diagnosis, atrophic, inactive, proliferative - weakly proliferative, proliferative - active proliferative, proliferative - disordered proliferative, secretory - cyclic type, secretory - progestational type (including stromal decidualization), menstrual type, simple hyperplasia without atypia, simple hyperplasia with atypia, complex hyperplasia without atypia, complex hyperplasia with atypia, carcinoma for Initial diagnosis and Safety diagnosis will be summarized separately by visits for the Safety Analysis Set.

Frequency counts (n), percentages and the 95% CIs of the additional pathological results including polyps, stromal tissue, metaplasia and cervical tissue for Safety diagnosis will be summarized separately by visits for the Safety Analysis Set.

Frequency counts (n), percentages and the 95% CIs of benign endometrium (including subcategory 1a with disordered proliferative as consensus diagnosis), simple hyperplasia without atypia, complex hyperplasia without atypia, simple hyperplasia with atypia, complex hyperplasia with atypia (including total for all hyperplasia), carcinoma will be summarized separately by visits for the Safety Analysis Set for Final/Consensus diagnosis. Worst-case analysis across all on-treatment visits will also be summarized for the Safety Analysis Set for the Final/Consensus diagnosis.

A listing will be provided of all subjects with all biopsy results from each pathologist, and the Initial, Safety diagnosis and Final/Consensus diagnosis for the Included Set.

For the exclusionary subjects due to disordered proliferative endometrium and worse, a listing of Patients with Abnormal Endometrial Biopsy will be provided with all biopsy results per pathologist, initial pathology report, safety and final diagnosis for the Included Set.

To analyze inter-reader variability, Kappa statistics (coefficient of agreement between the reviewing pathologists) will be calculated. The simple (Cohen) kappa coefficient measure of

---

interrater agreement will be used to estimate agreement among all the pair-wise comparisons of readers. For the comparison of consensus diagnosis (between readers 2, 4 and 5), safety diagnosis (between readers 1, 2, 4) and for the overall comparison (between all readers), the subject level comparison/repeated nature of the biopsies is not of interest, therefore the SAS MAGREE macro will be used to calculate Fleiss's kappa statistics for nominal responses.

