**Appendix 4 Modified Clinical Global Impression**

The Modified CGI to be used in this study is presented below

---

**Appendix 5      Histologic Descriptions Recommended for use when Reading  
Endometrial Biopsy Slides****Histologic Characteristics of the Endometrium**

0. No tissue
1. Tissue insufficient for diagnosis
2. Atrophic
3. Inactive
4. Proliferative
  - a. Weakly proliferative
  - b. Active proliferative
  - c. Disordered proliferative
5. Secretory
  - a. Cyclic type
  - b. Progestational type (including stromal decidualization)
6. Menstrual type
7. Simple hyperplasia without atypia
8. Simple hyperplasia with atypia
9. Complex hyperplasia without atypia
10. Complex hyperplasia with atypia
11. Carcinoma (specify type)

If there are any polyps, please specify the type or types.

- Functional
- Atrophic
- Hyperplastic without atypia
- Hyperplastic with atypia
- Carcinomatous

If there is any stromal tissue, please specify the type or types.

- Smooth muscle tissue, normal
- Features suggestive of adenomyoma
- Features suggestive of stromal nodule
- Sarcoma (specify type)

If there is any metaplasia, please specify the type or types.

- Squamous
- Papillary
- Eosinophilic
- Ciliated
- Mucinous
- Syncytial
- Other type (specify type)

If there is any cervical tissue, please specify the type or types.

- Fragments of negative cervical epithelium
- Endocervical polyp
- Atypical endocervical glandular epithelium
- Atypical squamous metaplasia
- Squamous dysplasia
- Cervical carcinoma

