**Table 8: Category Indicators for Final Diagnosis**

Category	Histologic Characteristics of the Endometrium
Category 1	0,1,2,3,4,5,6
Category 2	7
Category 3	9
Category 4	8
Category 5	10
Category 6	11

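### Final/Consensus categories use main histology codes only, so a hyperplastic or carcinomatous polyp, or a sarcoma, can be classed as benign endometrium unless readers repeat it in the main code

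*SAP*

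**What the plan says.** - SAP Appendix 5 gives a numbered list of main histology codes, 0 to 11, followed by unnumbered lists of further findings. One begins "If there are any polyps, please specify the type or types" and offers functional, atrophic, two hyperplastic grades (with and without atypia) and carcinomatous. Sarcoma is an entry in the stromal list.
- SAP 7.7.1.12.1 (Evaluation of Endometrial Tissue) says that "Endometrial polyps will be fully characterized as to the glandular proliferation and atypia", but gives no rule that carries the result into a diagnosis category. Protocol 10.4.8 has the same instruction and the same gap.
- SAP 7.7.1.12.1 (On Study Biopsies) also says that "Benign Endometrium has been defined as any of the following readings" and then lists codes 0 to 6, with no exception for an accompanying polyp or stromal malignancy.
- "Table 8: Category Indicators for Final Diagnosis" assigns codes 0–6, 7, 9, 8, 10 and 11 to Categories 1 to 6. It has no other row.
- On the endpoint, SAP 7.7.1.12.1 states: "The Final/Consensus diagnosis will be used for the analysis of the endometrial safety endpoint". SAP 7.7.1.12 attaches a two-sided 95% CI to the hyperplasia/carcinoma frequency.
- SAP 7.7.1.12.2 plans the polyp and stromal table for the Safety diagnosis: "additional pathological results including polyps, stromal tissue, metaplasia and cervical tissue for Safety diagnosis will be summarized separately by visits". The Safety diagnosis uses readers 1, 2 and 4; the Final/Consensus diagnosis uses readers 2, 4 and 5.

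**The concern.** The readers are asked to grade exactly the pathology that the endometrial endpoint is meant to detect, but one of the places where they record it does not feed the endpoint. Whether a hyperplastic or carcinomatous polyp counts then depends on each pathologist's habit: if the grade is also entered as a main code from 7 to 11, it counts; if the surrounding endometrium is coded atrophic and the grade goes only in the polyp field, it does not.

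Non-hysterectomized women in the Safety Study part receive E4 20 mg, with progesterone only after E4 ends, so this rate is a central safety description. Any error runs one way: an unmapped finding can remove a woman from the numerator and cannot add one. A rule chosen after the results are known would be open to challenge.

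**Working it through.** **Mapping check.** The plan gives no figure to reproduce on this point, so the check compares the two lists.

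1. Table 8 uses codes {0–6} ∪ {7} ∪ {9} ∪ {8} ∪ {10} ∪ {11} = {0, …, 11}, each once. Every main code is mapped. No polyp type and no stromal type is mapped.
2. Take main code 2 (atrophic) with a carcinomatous polyp. Code 2 belongs to Category 1, and no other rule applies. The reader's category is benign.
3. SAP 7.7.1.12.1 takes agreement of at least two adequate readings and, failing agreement, the most severe. With three adequate readings, the case ends as benign if at least two consensus readers leave the finding out of the main code. If two readers enter it in agreement, or no two readers agree, it is counted.

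**Do other outputs recover it?**

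- The polyp/stromal table is built on the Safety diagnosis (readers 1, 2, 4). Reader 5's polyp findings enter no planned summary table.
- The biopsy-based AESI list (SAP 7.7.1.1) covers disordered proliferative endometrium, the four hyperplasia types and carcinoma. It has no polyp or sarcoma entry.
- The listing of all biopsy results by pathologist (SAP 7.7.1.12.2) would show the case, but a listing does not enter a rate.

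**Size, for illustration.** Inputs: about 200 non-hysterectomized women (SAP 3.1) and 50% dropout at 12 months (Protocol 8.1). 200 × (1 − 0.50) = 100. This is an assumed evaluable number, and it may be low: women who stop early after at least 12 weeks of treatment also have a biopsy (Protocol 10.4.8), and the worst-case analysis includes unscheduled biopsies. The SAP names no interval method, so Clopper-Pearson is assumed: for x = 0 the upper bound is 1 − 0.025^(1/n); for x ≥ 1 it is the 0.975 quantile of Beta(x + 1, n − x).

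| Evaluable n | 0 events: upper bound | 1 event: estimate, upper bound | Change in upper bound |
|---|---|---|---|
| 70 | 5.13% | 1.43%, 7.70% | 7.70 − 5.13 = 2.57 points |
| 100 | 3.62% | 1.00%, 5.45% | 5.45 − 3.62 = 1.83 points |
| 200 | 1.83% | 0.50%, 2.75% | 2.75 − 1.83 = 0.92 points |

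At n = 100 a second such case gives 2.0% with an upper bound of 7.04%. The documents give no frequency for these polyps and no indication of how often readers would omit the grade from the main code, so no expected bias can be calculated.

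**The case against.** The strongest reply is that pathologists will not behave this way. Codes 7 to 11 are available for tissue from a polyp, the protocol presents the polyp list as additional to the main code, and one reader's omission is not enough. Figure 2 of the SAP, which is said to define the Final/Consensus categories, is not shown in the available text. It may hold more than Table 8, since the SAP mentions a subcategory 1a that Table 8 lacks. Protocol 10.4.8 also places detailed assessment procedures in separate manuals. Presence of an endometrial polyp is an exclusion criterion, which should make such cases rarer. The findings are not hidden either: two of the three consensus readers contribute to the Safety table, and every reading is listed. Finally, this SAP covers a single-arm part in which the endometrium is a secondary objective, no formal test is planned, and the current text sets no threshold for the interval.

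Most of this stands, and it limits the point to a possible bias. It does not remove the gap: neither document requires the polyp grade to be repeated in the main code, and Table 8, titled "Category Indicators for Final Diagnosis", covers every main code and nothing else. If a manual contains the rule, one SAP sentence citing it would answer much of the point.

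Two stronger readings are tempting. A reader might infer that the rate *is* biased low; the documents do not support that, because the loss depends on reader practice that they do not describe. A reader might also infer that sarcoma is wrongly missing from the hyperplasia/carcinoma rate; sarcoma is not carcinoma, so its absence follows from the rate's definition. The defect there is the possible benign label.

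**Conclusion.** The written derivation can class a hyperplastic or carcinomatous polyp, or a sarcoma, as benign endometrium when the main code is 2 to 6. For polyps, the hyperplasia/carcinoma rate could therefore be biased low, and this route cannot bias it high. One woman matters at these event counts: from zero events, the upper bound rises by 1.83 points at n = 100 and by 0.92 points at n = 200. Those sizes rest on an assumed denominator and an assumed interval method, and they apply only if at least two consensus readers leave the grade out of the main code. The conclusion also assumes that neither Figure 2 nor the biopsy manuals already contain a mapping rule. No planned test or decision depends on this interval, so this is an inexpensive improvement to prespecify, not a flaw that invalidates the analysis.

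**What to change.** In SAP 7.7.1.12.2, before database lock:

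1. Tabulate polyp and stromal findings for the consensus readers (2, 4 and 5), alongside the Safety table already planned.
2. Add a prespecified sensitivity hyperplasia/carcinoma rate with a 95% CI. For each reader, take the worse of the main code and the polyp grade, then form the consensus. Carcinomatous polyps count as carcinoma. Hyperplastic polyps count in the total-hyperplasia row, split by atypia; they should not be forced into simple or complex, because the polyp list does not make that distinction.
3. Report sarcoma in its own malignant row, neither as benign nor as carcinoma.
4. Show the rate with and without polyp-only cases, so that the effect of the rule is visible.

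The data are already collected. The cost is one derivation rule and a few extra table rows, and the rate may come out less favourable.
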